### Handling of missing data

After the handling of intercurrent events explained above, missing data will be managed in two steps as given below.

- 1) Non-responder imputation will be performed for all scheduled visits following participant discontinuation from the study with the reason 'lack of efficacy'.
- 2) LOCF approach will be applied for all missing visits, except for missing data that arises following study discontinuation with reason 'lack of efficacy'.

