6.10 Early Withdrawal from Study

6.10.1 Discontinuation of Study Treatment

6.10.1.1 Permanent Discontinuation of Study Treatment

[REDACTED]

[REDACTED]

[REDACTED]

[REDACTED]

[REDACTED]

[REDACTED]

[REDACTED]

- [REDACTED]
- [REDACTED]
- [REDACTED]
- [REDACTED]
- [REDACTED]
- [REDACTED]
- [REDACTED]

- Participant receives an investigational drug (other than IMG-007)
- Lack of efficacy/activity of the study treatment, defined as inadequate improvement in disease activity based on investigator's clinical judgment
- Physician decision
- Study is stopped by the Sponsor or health authority.

Note that discontinuation of study treatment does not represent withdrawal from the study. If study treatment is discontinued early, efforts should be made to perform the remaining study visits through EOS.

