6.10.2 Participant Withdrawal from the Study

In accordance with the Declaration of Helsinki and other applicable regulations, a participant has the right to withdraw from the study at any time at his/her own request or may be withdrawn at the discretion of the investigator for safety, compliance or administrative reasons.

A participant might withdraw from the study for any of the reasons below:

- Voluntary withdrawal of consent or study participation, at any time
- A participant's failure to comply with the protocol requirements or study-related procedures
- An intercurrent or safety event which, in the opinion of the investigator, requires the withdrawal of the participant
- Lost to follow-up
- Death

If a participant cannot or will not continue in the trial, the participant should complete the EOS visit procedures instead of the planned visit. All information, including the reason for early withdrawal, will be recorded in the participant's study records and in the case report form (CRF).

For participants who are lost to follow-up or withdraw their consent to participate in the study, the procedures of withdrawal from the study will no longer apply.

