## 5.5 Participant Disposition

Summaries will be provided for the following data in each treatment group for the full study sample (i.e., all screened participants who signed informed consent):

- The number and percentage of participants screened, and who failed screening, along with the reasons for screen failure. (This will be reported only in the overall group.)
- The number and percentage of participants included in each treatment group as well as in each study analysis set.
- The number and percentage of participants who completed the 4-week dosing period, discontinued the 4-week dosing period with the reason for discontinuation, completed the 16-week treatment period, discontinued 16-week treatment period with reason for discontinuation, completed the study, and discontinued the study with reason for discontinuation, consented for the extended follow-up, completed the extended follow-up, and discontinued the extended follow-up with reason for discontinuation.

A summary will be provided for major protocol deviations by deviation category and treatment group for the safety analysis set. The protocol deviations flagged as ‘CSR Reportable’ will be classified as major protocol deviations.

The following listings will be provided.

- The participant disposition listing comprises various details, including the date of informed consent form (ICF) signing, ICF and protocol versions, enrolment or screen failure dates, and the completion/discontinuation date of the 4-week dosing period, date of 16-week treatment period/discontinuation, reason for discontinuation, study completion status, date of study completion, among other factors.
- A listing of screen failures with inclusion criteria not met and/or exclusion criteria met.
- Listing of protocol deviation.

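### Non-responder imputation for SALT30 depends on a reason the protocol does not list for leaving the study; other leavers get LOCF, with no sensitivity analysis

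*SAP*

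**What the plan says.** SAP 5.7.2.2 first handles intercurrent events for the binary endpoints. Data collected after treatment discontinuation are used as observed (treatment policy), and a participant who starts any prohibited medication is a non-responder from then on. Missing data are then handled in two steps:

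- Step 1: "Non-responder imputation will be performed for all scheduled visits following participant discontinuation from the study with the reason" lack of efficacy.
- Step 2: "LOCF approach will be applied for all missing visits, except for missing data that arises following study discontinuation with reason" lack of efficacy.

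The same section prespecifies no sensitivity analysis for these endpoints and leaves any to post-hoc choice.

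Protocol 6.10.2 introduces its list with "A participant might withdraw from the study for any of the reasons below" and gives five: voluntary withdrawal, failure to comply, an intercurrent or safety event, loss to follow-up, and death. Lack of efficacy is found in Protocol 6.10.1.1 instead. There, "Lack of efficacy/activity of the study treatment, defined as inadequate improvement in disease activity" in the investigator's judgement is a reason for permanently stopping treatment, and the section adds that "discontinuation of study treatment does not represent withdrawal from the study".

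SAP 5.5 tabulates reasons for leaving the study without defining the categories. As separate items it counts those who consented to the extended follow-up, "completed the extended follow-up, and discontinued the extended follow-up with reason for discontinuation".

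**The concern.** Step 1 looks like protection against informative dropout, but its trigger is not one of the protocol's listed reasons for leaving the study. Someone who leaves because hair is not regrowing may be recorded as a voluntary withdrawal, which sends the missing visits to LOCF. Step 1 also does nothing, even with a matching code, for a responder who leaves for another reason and whose later status is unknown.

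At stake is the SALT30 proportion at Week 24 and beyond. The trial is open label with no control arm, so no comparator shares an error in handling leavers. With 6 and 24 participants per cohort, one or two carried-forward responses change the reported rate visibly.

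**Working it through.** The documents state no SALT30 rate or dropout rate, and the sample-size text is redacted, so there is no figure of the plan's own to reproduce. The check compares the texts and then sizes the effect.

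**1. Which rule reaches which participant (SAP 5.7.2.2 against Protocol 6.10)**

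| Situation | Rule for later SALT30 visits |
|---|---|
| Stops treatment, stays in the study | Observed data used; step 1 not triggered |
| Starts a prohibited medication | Non-responder from then on |
| Leaves the study, reason recorded as lack of efficacy | Non-responder (step 1) |
| Leaves for any of the five reasons in Protocol 6.10.2 | LOCF (step 2) |
| Misses a visit and returns | LOCF (step 2) |

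Only the third row uses step 1, and its reason is not in the protocol's study-withdrawal list.

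**2. What LOCF carries**

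Protocol 4.1.2 asks leavers to complete the Week 16, Week 24 or Week 36 visit at withdrawal, and SALT is assessed at all three. Where that happens, LOCF carries the status at exit. Protocol 6.10.2 lifts the withdrawal procedures for participants lost to follow-up or withdrawing consent. For them the last scheduled SALT may be some weeks old.

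**3. Size per participant**

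Inputs: 6 participants in Cohort 1 and 24 in Cohort 2 (Protocol 4.1), so 30 pooled. If k leavers are carried as responders rather than set to non-response, the proportion rises by k/n. For k = 1:

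- Cohort 1: 1/6 = 16.7 points
- Cohort 2: 1/24 = 4.2 points
- Pooled: 1/30 = 3.3 points

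**4. Illustration in Cohort 2, on assumed inputs**

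Assume 6 responders among completers and 4 leavers. Non-response for every leaver gives 6/24; LOCF gives (6 + k)/24. Intervals are 95% Clopper-Pearson, as the SAP specifies.

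| k carried as responders | SALT30 | 95% CI |
|---|---|---|
| 0 (same as non-response for all) | 6/24 = 25.0% | 9.8 to 46.7 |
| 1 | 7/24 = 29.2% | 12.6 to 51.1 |
| 2 | 8/24 = 33.3% | 15.6 to 55.3 |
| 3 | 9/24 = 37.5% | 18.8 to 59.4 |
| 4 | 10/24 = 41.7% | 22.1 to 63.4 |

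With 2 to 6 leavers assumed, the largest possible difference is 2/24 = 8.3 to 6/24 = 25.0 points, and the smallest is 0. In Cohort 1, one carried responder turns 1/6 (16.7%) into 2/6 (33.3%).

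**5. Weeks 30 and 36**

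SAP 5.5 counts those who consented to the extended follow-up, and Protocol 11.3.7 allows completion at Week 24 or Week 36 as applicable. Some participants may therefore finish at Week 24. Step 2 covers all missing visits, so read literally it carries their Week 24 status to two visits they were never due to attend.

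**The case against.** Four stronger readings are tempting, and the documents do not support them.

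- **Step 1 can never act.** Protocol 6.10.2 does not call its list closed, and Protocol 7.1.5 has the investigator record a primary criterion for termination. The eCRF code list is not in the documents and may offer lack of efficacy. What stands is that step 1 may rarely or never trigger.
- **All early leavers keep a favourable last status.** Prohibited-medication users are already non-responders, and many leavers should have an exit SALT. A person who leaves because hair is not growing would usually be a non-responder when last seen, so both rules agree. The difference comes mainly from responders who leave for other reasons, whom step 1 would miss even with a matching code.
- **LOCF must bias SALT30 upward.** The disease is described as relapsing and dosing ends at Day 29, but Protocol 2.5.1 expects slow regrowth and a possibly enduring effect. Carrying an early status forward could also understate response, so the direction is open.
- **Step 1 cannot reach exits from the extended follow-up.** SAP 5.5 is a disposition table, not an imputation rule. Protocol 4.2 ends the study after the extended follow-up, and SAP 5.8.1 counts study discontinuation in its 36-week summary. The text is ambiguous rather than exclusive.

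It is also fair to say that non-response for any reason is a conservative choice, not the only valid one, and that the secondary endpoint is a continuous SALT change. These points limit the weight of the concern. They do not supply a sensitivity analysis or verify a carried response.

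**Conclusion.** The mismatch between the SAP trigger and the protocol's study-withdrawal reasons is real. As written, a responder who leaves for a reason other than recorded lack of efficacy, without starting prohibited medication, stays a responder at every later visit, and no planned analysis shows how much the result depends on this.

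The size is 16.7 points per such participant in Cohort 1 and 4.2 in Cohort 2. It is zero if all leavers were non-responders when last seen. The total rests on the number of leavers and their last status, neither of which the documents give, so the illustration shows scale and is not a forecast. SALT30 is a key exploratory endpoint reported descriptively, which makes the impact low to moderate. The change is still worth making because it is cheap and does not depend on the eCRF codes.

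**What to change.** Amend SAP 5.7.2.2 before database lock:

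- **Step 1:** remove the reason condition. Apply non-response at scheduled visits after withdrawal from the study, or from the extended follow-up once entered, for any reason.
- **Step 2:** keep LOCF only for intermittent missed visits, meaning those with a later observation.
- **Weeks 30 and 36:** do not impute for participants who completed Week 24 and never entered the extended follow-up. Report these visits among participants who entered it, with that denominator shown.
- **Sensitivity analysis:** report the current LOCF rule alongside.

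The SAP should also state how a missed last visit without a recorded withdrawal is counted, since it is neither intermittent nor after withdrawal.

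The cost is SAP wording, a programming flag and one extra table. Response rates may be slightly lower, and the rule is conservative if responses persist after leaving. The Week 30 and 36 rates will describe only those who continued and will not be directly comparable with Week 24 in the full set.

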12.3 Informed Consent Process

The investigator must obtain informed consent of a subject and/or a subject's legal representative prior to any study related procedures.

Documentation that informed consent occurred prior to the participant's entry into the study and of the informed consent process should be recorded in the participant's source documents including the date. The original ICF signed and dated by the participant, and by the person consenting the participant prior to the participant's entry into the study, must be maintained in the investigator's study file and a copy given to the participant. In addition, if a protocol is amended and it impacts the content of the informed consent, the ICF must be revised. Participants participating in the study when the amended protocol is implemented must be re-consented with the revised version of the ICF. The revised ICF signed and dated by the participant and by the person consenting the participant must be maintained in the investigator's study files and a copy given to the participant.

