## 5. STATISTICAL METHODS

For continuous variables, at the reported visits or in overall summary, descriptive statistics will consist of: number of non-missing observations (n), mean, median, standard deviation (SD), minimum, and maximum. It is to be noted that number of participants with observations could include participants with data that were observed as well as those that were imputed for specific types of missing data or determined based on handling of intercurrent events, as explained in later sections.

For categorical variables, frequencies and percentages will be displayed for each category.

In the context of efficacy-related tables, percentages will be calculated based on the denominator of number of participants with data depending on the handling of intercurrent events as well as imputations of missing data as explained in the later sections. For non-efficacy tables, percentages will be calculated based on the corresponding analysis population unless otherwise specified in the mock shell.

Listed below are some subgroups for potential exploratory subgroup analysis:

- Race (Black/African American vs. Non-Black/Non-African American)
- Age group (<30 years old vs.  $\geq 30$  years old)
- SALT Score at baseline (50 to <75, 75 to <95, 95 to 100)
- Age at disease onset ( $\leq 12$  years old vs.  $> 12$  years old)
- Presence of autoimmune comorbidities (Yes vs. No)
- Presence of atopic comorbidities (Yes vs. No)
- Duration of current episode (< 2 years vs.  $\geq 2$  years)
- Baseline elevated IgE (Yes vs. No)

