### 5.7.2 Analysis of Key Exploratory Efficacy Variables

#### 5.7.2.1 *Continuous efficacy endpoints*

All continuous exploratory efficacy endpoints will be analyzed using the same approach as that used for the main analysis of percentage change in SALT from baseline to Week 24.

For the timepoints beyond Week 24, separate MMRM models will be developed to include all the post-baseline visits until Week 36. However, the estimates and p-values will be reported only for the timepoints beyond Week 24 from these models. The results of earlier timepoints will be reported from the models up to Week 24.

ANCOVA will be utilized as explained in the main analysis section if the MMRM model fails to converge.

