#### 5.7.2.2 *Responder type (binary) efficacy endpoints*

The responder type (binary) endpoints will be reported using frequency and percentage by treatment along with the 95% Clopper-Pearson exact confidence interval for the proportion.

Based on the estimand framework introduced in [ICH E9\(R1\)](#), additional details relating to the definition of the estimand is proposed.

Handling of intercurrent events (for responder type binary endpoints) of treatment discontinuation and prohibited medication:

- *Treatment discontinuation*: Treatment policy strategy will be followed. i.e., all the collected data available after treatment discontinuation will be included in the analysis.
- *Any prohibited medication*: Participant will be reported as non-responder at all the visits occurring after the prohibited medication start.

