### Sensitivity analysis

No prespecified sensitivity analyses will be performed. Additional post-hoc sensitivity analysis will be considered as appropriate later.

Line plots will be included to depict responder-type of endpoints of SALT for each treatment group. The X-axis will feature visits, and the Y-axis will represent the proportion of participants, expressed as a percentage.

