### **5.7.3 Analysis of Other Exploratory Efficacy Variables**

All the continuous exploratory variables will be analyzed using descriptive statistics (n, mean, median, standard deviation, minimum, and maximum).

All the binary exploratory variables will be summarized with frequency and percentages.

Intercurrent events will be handled as described in section [5.7.1](#) and [5.7.2.2](#) based on the characteristics of the analysis variable. No additional missing data imputations and sensitivity analysis are applicable for other exploratory endpoints.

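### As written, SAP 5.7.2.2 carries the last SALT30 status to Weeks 30 and 36 for participants who finish at Week 24 without entering the extended follow-up, with no prespecified check

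*SAP*

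**What the plan says.** **The endpoint.** SAP 4.5.2.1 lists SALT30 by visit as a key exploratory endpoint. The SALT windows in SAP Appendix 11.3 include Week 30 and Week 36.

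**The missing-data rule.** SAP 5.7.2.2 has two steps. Step 1 scores scheduled visits as non-response after a participant leaves the study for lack of efficacy. Step 2 reads: "LOCF approach will be applied for all missing visits, except for missing data that arises following study discontinuation with reason" lack of efficacy. Separately, anyone who starts a prohibited medication is a non-responder at all later visits.

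**What enters the result.** SAP 5 bases efficacy percentages on a "denominator of number of participants with data depending on the handling of intercurrent events as well as imputations of missing data", so imputed values can count. SAP 5.7.2.2 adds the "95% Clopper-Pearson exact confidence interval for the proportion".

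**Checks.** For the binary endpoints: "No prespecified sensitivity analyses will be performed. Additional post-hoc sensitivity analysis will be considered as appropriate later".

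**The extension.** Protocol 2.5.1 says the extended follow-up was added to look for further improvement between Week 24 and Week 36. Protocol 12.3 says: "Participants participating in the study when the amended protocol is implemented must be re-consented with the revised version of the ICF". SAP 5.5 counts those who consented to, completed and discontinued the extension. Protocol 11.3.7 lets a participant's completion be Week 24 or Week 36, depending on which applies.

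**The protocol's base method.** Protocol 11.3.3 says efficacy is in general described on observed data. The synopsis adds that imputation methods are explored as well as the observed-value method.

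**The concern.** The documents foresee participants who complete Week 24 and stop there. Such a participant has not left for lack of efficacy, so neither step 1 nor the exception in step 2 applies. The literal rule therefore turns the last status into a Week 30 and a Week 36 result, 6 and 12 weeks after the Week 24 visit.

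Weeks 30 and 36 exist to show whether response changes after Week 24. A carried status answers that question by assumption: relapse is missed, and so is continued regrowth. The SAP also plans a figure: "Line plots will be included to depict responder-type of endpoints of SALT for each treatment group". With enough carried values its last stretch would look flatter than the assessed data, and the reported n would exceed the number actually assessed. No second version of the result is prespecified that would let a reader see this.

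**Working it through.** **The plan's own figure.** None is visible to reproduce: the sample-size justification is redacted and no SALT30 rate is given. The cohort sizes agree with the stated total (6 + 24 = 30).

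**Tracing one participant through the rule.** Suppose someone completes Week 24, declines the extension and has used no prohibited medication.
1. Prohibited-medication rule: does not apply.
2. Step 1 (left the study for lack of efficacy): does not apply.
3. Step 2 (LOCF for missing visits): applies, and its only exception does not.
4. Denominator in SAP 5: the carried value counts, and so enters the exact interval.

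No visible sentence limits Weeks 30/36 to participants who entered the extension.

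**Inputs for the illustration.** N = 24 comes from the documents (Cohort 2). The number not entering, k, the 25% response rate and the 12.5-point change are assumptions.

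**Precision and what the data allow.** Suppose LOCF reports 6/24 (25.0%) and entrants also respond at 25%. Intervals are two-sided 95% Clopper-Pearson. The range for the true Week 36 rate in all 24 is (observed responders)/24 to (observed responders + k)/24.

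| k | Observed | Exact 95% CI | Width (points) | Range for all 24 |
|---|---|---|---|---|
| 0 | 6/24 | 9.8–46.7% | 36.9 | 25.0% |
| 4 | 5/20 | 8.7–49.1% | 40.4 | 5/24 to 9/24 = 20.8–37.5% |
| 8 | 4/16 | 7.3–52.4% | 45.1 | 4/24 to 12/24 = 16.7–50.0% |
| 12 | 3/12 | 5.5–57.2% | 51.7 | 3/24 to 15/24 = 12.5–62.5% |

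Under LOCF the reported interval is the k = 0 row whatever k is.

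The narrowing is not universal. If 6/24 is made of 3/20 observed plus 3 carried responders, the observed interval (3.2–37.9%, width 34.7) is narrower than the LOCF one. The same holds for 1/16 observed plus 5 carried (0.2–30.2%, width 30.1).

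**Change hidden.** If entrants and non-entrants change alike, shown change = true change × (1 − k/24). For a true change of 12.5 points:
- k = 4: 12.5 × 20/24 = 10.4 points
- k = 8: 12.5 × 16/24 = 8.3 points
- k = 12: 12.5 × 12/24 = 6.25 points, that is, half

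**Direction.** Take k = 12 and a Week 24 rate of 1/3 in both groups, so 4 of the 12 carried are responders.
- Entrants fall to 1/6: LOCF (2 + 4)/24 = 25.0%; observed 2/12 = 16.7%.
- Entrants stay at 1/3: LOCF (4 + 4)/24 = 33.3%; observed 4/12 = 33.3%.
- Entrants rise to 1/2: LOCF (6 + 4)/24 = 41.7%; observed 6/12 = 50.0%.

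LOCF pulls the estimate toward Week 24, so the error can go either way.

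**The case against.** **The literal reading may not be the intended one.** The extension is consented to separately and completion can be at Week 24. Weeks 30/36 could therefore be regarded as not applicable, rather than missing, for those who stop there. This stands as a caveat. The visible SAP does not say it, however, and a programmer following the text would carry forward.

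**Evidence of much non-entry is thin.** Protocol 4.1.2 gives each cohort four periods including the extension, and Protocol 7.1.6 expects participants to return for it. The re-consent requirement shows a decision point, not refusals. The amendment history is redacted, so the timing of the extension relative to anyone's Week 24 is unknown. Cohorts also start in sequence, so early completers would more naturally fall in the six-person Cohort 1. All of this stands: the values of k above are illustrations, not forecasts.

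**A tempting comparison cannot be checked.** A reader might infer that SALT30 at Week 36 would rest on different participants from the continuous SALT results, since SAP 5.7.2.1 says: "For the timepoints beyond Week 24, separate MMRM models will be developed to include all the post-baseline visits until Week 36". The documents do not support that inference. The missing-data and sensitivity text of SAP 5.7.1 is not visible, and SAP 5 allows imputed values in continuous summaries. SAP 5.7.3 does say of the remaining endpoints, "No additional missing data imputations and sensitivity analysis are applicable for other exploratory endpoints", but that does not settle how continuous SALT is handled.

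**Observed cases have faults too.** Entrants may be selected, and switching to them after Week 24 changes the population along the plotted line. This stands, and is why more than one version should be shown. The bodies of SAP 7.1 and 7.2 and the mock shells are also unavailable, so the absence of an observed-case result is judged on visible text only.

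**Conclusion.** The concern holds on the visible text, as a minor point. Read literally, SAP 5.7.2.2 counts a carried status as a Week 30 and Week 36 SALT30 result for non-entrants. It prespecifies no check and shows no observed-case result, although the protocol takes observed data as its base.

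The size depends wholly on the number of non-entrants, which the documents do not give, and it is nil if everyone enters and stays. With half of Cohort 2 not entering and 25% response in both groups, the reported interval would be 51.7 − 36.9 = 14.8 points narrower than the assessed participants support. Half of any common change would be hidden.

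A reader might also infer that Week 36 response is overstated, or that the interval is always too narrow. Neither follows: the bias can run either way, and the interval can be wider than the observed one when most carried participants are responders.

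The point is confined to one exploratory endpoint at two late visits, in a study whose efficacy analyses are largely descriptive. The Week 24 secondary endpoint is unaffected.

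**What to change.** In SAP 5.7.2.2:

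(a) State that LOCF is not applied at Weeks 30/36 to participants who did not enter the extended follow-up. Say whether this includes those who left before Week 24 for reasons other than lack of efficacy.

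(b) Report observed-case SALT30 at Weeks 30/36, keeping the existing non-responder rules for prohibited medication and lack-of-efficacy leavers. Give the numbers entered and assessed at each visit. Beside it, show the LOCF result limited to entrants, so that those who enter and later drop out are still carried there.

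(c) Replace the statement that no sensitivity analysis is prespecified with one named analysis: every missing Week 30/36 visit is set to non-response, with all dosed participants as denominator, labelled as a conservative bound.

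The cost is a few sentences of SAP text and some table rows, with no new data. The downsides are fewer participants and usually wider intervals at Weeks 30/36, possible selection among entrants in the observed-case result, and possible understatement of response in the bound.
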